# 7.3 Clinical Laboratory Assessments

Change from baseline values and shift tables will be presented for all clinical laboratory assessments except urinalysis. All clinical laboratory assessment data will be listed.

- Chemistry and metabolic assessments will be conducted at Screening, Baseline, Day 1, Weeks 2, 4, 6, 8, 12, 16, 20, 24, 36, 48, Months 15, 18, 21, 24, 27, 30, 33, and 36/EOS and at any Early Termination Visit.
  - The serum chemistry panel includes Na, K, Ca, HCO3, Cl, and P. The metabolic panel includes BUN, creatinine, glucose, and uric acid.
- Hematology assessments will be conducted at Screening, Baseline, Day 1, Weeks 2, 4, 6, 8, 12, 16, 20, 24, 36, 48, Months 15, 18, 21, 24, 27, 30, 33, and 36/EOS and at any Early Termination Visit.
  - The hematology panel includes a complete blood count with differential and platelets.
- Urinalysis assessments with microscopic examination include glucose, protein, bilirubin, blood, pH, and specific gravity.
  - Urinalysis assessments will be conducted at Screening, Baseline, Day 1, Weeks 2, 4, 6, 8, 12, 16, 20, 24, 36, 48, Months 15, 18, 21, 24, 27, 30, 33, and 36/EOS and at any Early Termination Visit.
- Liver assessments will be conducted at Screening, Baseline, Day 1, Day 7 (2x/week), Weeks 2, 4, 6, 8, 12, 16, 20 (2x/week), 24, 28, 32, 36, 40, 44, 48, 52, Months 15, 18, 21, 24, 27, 30, 33, 36/EOS, and at any Early Termination Visit.
  - The liver panel includes total and direct bilirubin, alkaline phosphatase, alanine aminotransferase (ALT), aspartate aminotransferase (AST), lactate dehydrogenase (LDH), albumin, and total protein. Liver panel parameters will be presented in figures for each subject.

Chemistry, metabolic, hematology, and liver assessment data will be summarized by presenting descriptive statistics of actual values and changes from baseline at each visit. Shift tables (change from baseline relative to the normal range) may be constructed for selected laboratory parameters.

CONFIDENTIAL Page 19 of 28

#### 7.4 Vital Signs

Vital sign data will be summarized by presenting descriptive statistics of actual values and changes from baseline at each visit. Vital sign parameters include respiratory rate, temperature, systolic blood pressure, diastolic blood pressure, and heart rate. Height and weight will be summarized by presenting descriptive statistics of actual values. Changes from baseline will be presented for weight. A listing of vital signs will also be provided.

Vital sign assessments will be conducted at Screening, Baseline, Days 0, 1, 7, Weeks 2, 4, 6, 8, 12, 16, 20, 24, 36, 48, Months 15, 18, 21, 24, 27, 30, 33, 36/EOS, and at any Early Termination Visit.

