8.1.3 Carcinogenicity

There is a risk that people who receive gene transfer may develop tumors derived from their genetically modified cells. This risk has been seen with viral gene transfer vectors that integrate randomly into the cellular DNA where they may affect genes controlling cell proliferation. The rAAV2/6 vector donor will integrate specifically in the albumin ZFN DSB site. In toxicity studies, no tumors were identified. For evaluation of liver carcinogenicity the current study adopts the hepato-cellular carcinoma (HCC) screening recommendation for high risk subjects (e.g., chronic hepatitis C or B), which includes monitoring AFP and liver MRI. Liver biopsy will be performed if there is an abnormal AFP and a >2 cm mass in the liver (El-Serag & Davila 2011).

8.2 **Prednisone (or Equivalent Corticosteroid)**

Prednisone is a glucocorticoid. Glucocorticoids are adrenocortical steroids, both naturally occurring and synthetic, which are readily absorbed from the gastrointestinal tract.

The following adverse reactions have been associated with the use of glucocorticoids:

- Thinning of bones (osteoporosis), which may lead to fractures or compressions, especially true of vertebral bodies (backbone).
- Loss of blood supply to bones (aseptic necrosis), which may cause severe bone pain, fractures (especially of the hip and shoulder), and which may require surgical correction.
- High blood pressure (hypertension).
- Increased pressure in the eye (glaucoma).
- Permanent clouding of vision in one or both eyes (cataracts).
- Weight gain with increased appetite and fluid retention.

- Facial fullness.
- Increase in body hair and acne, and tendency to easy bruising and thinning of the skin.
- Increased risk of infections while on high dose continuous steroid therapy.
- Interference with growth.
- Muscle cramps and joint pain.
- Changes in the menstrual cycle.
- Elevations in blood sugar (diabetes).
- Suppression of adrenal glands' ability to make necessary cortisone at times of stress (adrenal insufficiency).
- Irritation of stomach and esophagus with possible ulcer type symptoms and, rarely, bleeding.
- Emotional disturbances.

Dietary guidelines will be provided to subjects while on prednisone or equivalent corticosteroid to help alleviate some of the side effects including blood sugar elevation, associated with the use of glucocorticoids (refer to the Study Reference Manual).

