9.5 Vital Signs

Vital signs, including height, weight, systolic/diastolic blood pressure, heart rate, respiratory rate, and temperature will be recorded. For details, refer to the Study Reference Manual.

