#### 4.7 Data Derivations and Transformations

No data derivations or transformations will be performed.

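### For Cohorts 5-8, no planned summary in SAP 7.4 sets height or weight against what is expected for age and sex, although Protocol 8.2 names growth and weight effects of the steroid

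*SAP*

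**What the plan says.** - **Harm named.** Protocol 8.2 gives a general list of glucocorticoid reactions. It includes "Interference with growth" and "Weight gain with increased appetite and fluid retention". The list is not specific to children.
- **Exposure.** Protocol 3.5 and Appendix 3 give all subjects prophylactic prednisone or an equivalent, tapered over about 20 weeks. SAP 3.1 plans Cohorts 5 and 6 at ages 12-17 and Cohorts 7 and 8 at ages 5-11, with follow-up to Month 36.
- **Collection.** Protocol 9.5: "Vital signs, including height, weight, systolic/diastolic blood pressure, heart rate, respiratory rate, and temperature will be recorded".
- **Analysis.** SAP 7.4 gives respiratory rate, temperature, blood pressure and heart rate both measured values and changes from baseline at each visit. Height and weight are handled separately: "Height and weight will be summarized by presenting descriptive statistics of actual values. Changes from baseline will be presented for weight". SAP 5.4 also tabulates baseline height and weight.
- **Derivations.** SAP 4.7: "No data derivations or transformations will be performed". Neither document names a growth velocity, a percentile or an age- and sex-standardised score.

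**The concern.** In an adult, a stable height and a raw weight change are readable as they stand. In a child the expected value moves with age, so a measured height or a raw change in kilograms means little without a reference. SAP 7.4 applies one rule to all ages. Height is also the one measure in that section without a change from baseline, so its cohort summary carries the full height difference between children.

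Elsewhere the SAP does use a norm for safety data: SAP 7.3 provides for laboratory shift tables relative to the normal range and for per-subject liver figures. Growth, which is also tied to a reaction the protocol names, has neither.

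At stake is how readable one paediatric safety display is. A modest slowing of growth could pass unremarked in the tables, and ordinary weight gain could be read as a steroid effect.

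**Working it through.** **Figures from the documents.** The maximum sample reproduces: 8 cohorts × 2, plus 8 × 2 possible additions, = 32. Cohorts 5-8 therefore hold 4 × 2 = 8 to 4 × 4 = 16 subjects, or 2-4 per cohort. The Appendix 3 course is 3 days (Day -2 to Day 0) + 19 × 7 = 136 days. The SAP states no hypothesis, so no power formula applies.

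**Assumptions, none of them in the documents.** Normal growth 4-7 cm/year; steroid loss 0.5-2 cm, complete by Week 24 and not recovered; normal weight gain 2-4 kg/year; between-child height SD 5-15 cm; SD of height change 1-2 cm.

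**1. Height against normal growth.** Expected gain = rate × time; observed gain = expected gain − loss.

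| Visit | Expected gain | With 0.5 cm loss | With 2 cm loss |
|---|---|---|---|
| Week 24 (rate × 24/52) | 1.8 to 3.2 cm | 1.3 to 2.7 cm | −0.2 to 1.2 cm |
| Month 36 (rate × 3) | 12 to 21 cm | 11.5 to 20.5 cm | 10 to 19 cm |

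At Week 24 a 2 cm loss falls outside the normal range, but a 0.5 cm loss largely overlaps it. By Month 36 even the 2 cm loss overlaps it from 12 to 19 cm. The loss is then 0.5/21 = 2% to 2/12 = 17% of expected growth. A raw height change alone would therefore not be enough at later visits; the expected value for age and sex is needed.

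**2. Cohort composition.** When one of n children leaves, the mean moves by (leaver's distance from the cohort mean)/(n − 1).
- n = 2, heights 20 cm apart (assumed): 10/1 = 10 cm.
- n = 4, leaver 10 cm from the mean (assumed): 10/3 = 3.3 cm.

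Protocol 3.4 allows transfer to the long-term study after 12 months, so departures are foreseeable. Change from baseline removes the starting-height difference. For two children growing at 4 and 7 cm/year, gains at Month 15 are 4 × 1.25 = 5.0 cm and 7 × 1.25 = 8.75 cm. Losing one then moves the mean change by (8.75 − 5.0)/2 = 1.9 cm.

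**3. Precision of a cohort mean (SE = SD/√n).**
- Measured height: 3.5-10.6 cm for n = 2; 2.5-7.5 cm for n = 4.
- Height change: 0.7-1.4 cm for n = 2; 0.5-1.0 cm for n = 4.

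**4. Weight.** Normal gain is 2 × 24/52 = 0.9 kg to 4 × 24/52 = 1.8 kg by Week 24, and 3 × 2 = 6 kg to 3 × 4 = 12 kg by Month 36. For a child at the 20 kg entry minimum (Protocol 4.2), the latter is 6/20 = 30% to 12/20 = 60% of baseline. The raw weight-change summary does not distinguish this from excess gain.

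**The case against.** The strongest reply is that nothing is hidden. SAP 7.4 adds: "A listing of vital signs will also be provided". Protocol 9.5 counts height and weight as vital signs, SAP 4 and 4.3 list subject data from all assessments, and SAP 5.4 provides a by-subject listing of baseline characteristics. With 2-4 children per cohort, each height change is one subtraction. Growth that an investigator judges to have worsened can also be reported as an adverse event under Protocol 10.1.1. All of this stands. A reader might infer that the plan conceals growth suppression or cannot show it. The documents do not support that, and a large loss could be visible in raw height near the end of the course.

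A reader might also infer that SAP 4.7 forbids standardised scores. Read with the rest of the SAP it does not. The SAP itself derives pre-dose mean baselines for GAG and IDS (4.3), study day (4.4), half-detection-limit values (4.5), annualised ERT use (6.2) and changes from baseline. SAP 4.7 is loose wording that needs aligning.

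Three further points stand:
- Growth is one line in a general steroid list. It is absent from the key anticipated risks in Protocol 12.2 and from the additional safety evaluations in Protocol 13.4. Its relevance to Cohorts 5-8 is a direct inference, not a statement in the text.
- Means that shift when a subject leaves affect every by-visit summary in this study.
- The documents show no child dosed. Protocol 1.5 reports six subjects at three doses and a recommendation to open Cohort 5.

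The reply does not show that the stated summaries suit growing subjects. A listing leaves each reader to supply the expected value for age and sex.

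**Conclusion.** The point holds as a minor gap in display. SAP 7.4 summarises paediatric height without change from baseline and weight without a reference, so no planned summary shows growth against expectation. The weakness is greatest at later visits. There, under the assumed rates, normal growth is several times any assumed loss (12 cm against 2 cm at the least favourable, a factor of 6).

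Those sizes depend wholly on assumed growth rates, steroid loss, weight gain and height spread. The text of SAP 7.4 does not depend on them. The practical effect depends on at least one subject in Cohorts 5-8 being dosed.

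It would go too far to expect the repaired display to isolate a steroid effect. Every subject receives both steroid and SB-913, all have MPS II, and there is no control arm. No endpoint, stopping decision or clinical rule changes.

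**What to change.** If any subject in Cohorts 5-8 is dosed:

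1. In SAP 7.4, add change from baseline in height at each visit at which height is measured.
2. Add age- and sex-standardised height and weight scores, actual and change, using a reference named in the SAP. Show them per subject by visit, since cohort means of 2-4 are fragile.
3. Reword SAP 4.7 so that it allows these scores and the derivations the SAP already makes. Keep the raw values in the listing.
4. State beside the display that, with no control arm, a falling score is a signal for review and cannot be attributed to steroid, SB-913 or disease.

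The cost is SAP wording and one extra table or figure from height, weight, age and sex already collected. The one real choice is the reference population. No procedure, dose or clinical rule is affected.

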# 7.5 Physical Examination

A listing will be provided for all physical examination abnormalities.

Physical examination assessments will be conducted at Screening, Baseline, Days 0, 1, 7, Weeks 2, 4, 6, 8, 12, 16, 20, 24, 36, 48, Months 15, 18, 21, 24, 27, 30, 33, 36/EOS, and at any Early Termination Visit.

# 7.6 Electrocardiogram (ECG)

A listing will be provided for all electrocardiogram (ECG).

Electrocardiogram (ECG) assessments will be conducted at Screening, Baseline, Days 7, Weeks 24, 48, Months 18, 24, 30, 36/EOS, and at any Early Termination Visit.

# 7.7 Echocardiogram (ECHO)

A listing will be provided for all echocardiogram (ECHO).

Echocardiogram (ECHO) assessments will be conducted at Screening, Week 48, Months 24, 36/EOS, and at any Early Termination Visit.

# 7.8 Neurologic Cranial Nerve Exam and Muscle Strength Test

The results of the Neurologic Cranial Nerve Exam and Muscle Strength Test will be provided in a listing. Change from baseline values will be presented for Muscle Strength Test. The number and percentage for Neurologic Cranial Nerve Exam will be presented.

Neurologic cranial nerve exam and muscle strength test assessments will be conducted at Baseline, Week 24, Week 48, Months 18, 24, 30, 36/EOS, and at any Early Termination Visit.

#### 7.9 Serial $\alpha$ -fetoprotein (AFP) Testing

Serial  $\alpha$ -fetoprotein (AFP) testing data will be summarized by presenting descriptive statistics of actual values and changes from baseline at each visit. A listing will be provided for all Serial  $\alpha$ -fetoprotein (AFP) testing.

Serial α–fetoprotein (AFP) testing assessments will be conducted at Screening, Weeks 4, 8, 12, 24, 48, Months 18, 24, 30, 36/EOS, and at any Early Termination Visit.

#### 7.10 Adrenocorticotropic Hormone (ACTH) Stimulation

The results of the ACTH stimulation tests will be listed.

CONFIDENTIAL Page 20 of 28

ACTH stimulation assessments will be conducted at Baseline (prior to prednisone) and Week 20.

#### 8. SMC ANALYSIS

An external SMC with appropriate medical and scientific expertise will have oversight of the study.

The SMC will be convened after the completion of each cohort to advise whether it is safe to proceed with the next dose cohort and to provide recommendations on pediatric dosing and expansion of any cohort. The SMC may also be convened at any time if there are excessive or unexpected toxicities associated with the conduct of the protocol. Specifically, the SMC will be convened if the following occurs:

- Any one Grade 3 or higher AE, or any two Grade 2 AEs in the same system organ class that last more than 2 weeks with therapy, provided these AEs are not related to the primary MPS II disease or treatment of the MPS II disease.
- SAE not related to the primary MPS II disease.
- Death of a subject.
- Development of a malignancy.

The SMC will then evaluate all data to advise whether the changes should be made to the study or whether accrual and dosing should be halted. In addition, no further dosing of subjects will be performed until a substantial amendment is submitted to the regulatory authority(ies) for review, and the amendment has been approved by the site IRB/IEC or equivalent. The SMC may also recommend changes to the enrollment of cohorts based on cumulative adult and pediatric safety and efficacy data from similar ongoing first-in-human clinical trials that are sponsored by Sangamo and that use in vivo rAAV2/6-based gene transfer of ZFNs. Specifically, study SB-318-1502 in MPS I subjects uses identical ZFNs components (SB-47171 and SB-47898) as the present study in combination with a different donor cDNA (encoding human alpha-iduronidase) (Clinicaltrials.gov NCT02702115). Given the similarities of the approaches, relevant data from study SB-318-1502 and other trials sponsored by Sangamo may be shared with the SMC to expand the clinical experience, particularly as it relates to safety and dose, and such data can be used by the SMC to inform its recommendations for the present study.

When no further enrolling or dosing decisions are required of the SMC, the SMC will no longer meet. Sangamo will continue to review subject safety data on an ongoing basis.

#### 9. SAMPLE SIZE AND POWER CALCULATIONS

This study will enroll up to 32 subjects (2 subjects in each of 8 cohorts, with potential enrollment of approximately 2 additional subjects in any cohort). The sample size for this study was not based on statistical considerations, but is considered sufficient to provide preliminary assessments of the safety and tolerability of SB-913 in subjects with MPS II, as well as biochemical changes related to the pathophysiology of MPS II. Subjects who prematurely discontinue the study prior to the 12 months of study follow-up (i.e., subjects who were enrolled

CONFIDENTIAL Page 21 of 28

but not dosed, were lost to follow-up, or discontinued prematurely for another reason) may be replaced at the discretion of Sangamo.

CONFIDENTIAL Page 22 of 28

# 10. APPENDICES

# 10.1 Appendix A: Schedule of Events

	Screening		Uaca	ital or Acute	Day	Τ							7	Weel	k									M	ntl	1			
	(p)	Baseline		re Facility	7	2	4	6	8	12	16	20	24	28*	32*	36	40*	44*	48	52*	15	18	21	24	27	30	33	36 EOS	
PROCEDURE	(win 3 months of Baseline)	(win 21 days prior to SB-913 infusion)	Day 0	Day 1	(+/-1 day)	(+	-/-2	day	s)				•	(+	(+/-1 week)							(+/-1 month)							ETV
Informed Consent	X					L																							
Medical History	X																										$\perp$		
Concomitant Medications	X	X	X	X	X	Х	Х	х	X	X	X	х	х	Х	Х	Х	Х	Х	х	х	х	х	х	х	х	Х	X	Х	X
Inclusion/Exclusion	X					Г	Γ	П	Т																		Т		
Demographics	X							П	$\top$		$\Box$																Т		
Physical Examination	X	X	X	X	X					X :		х	х			Х			Х		Х	х	х	х	х	Х	X	Х	X
Vital Signs (a)	X	X	X	X	X					X :		- 1	Х			Х			Х		Х		х	Х	Х	Х	X	Х	X
AE Assessment	X	X	X	X	X	Х	Х	Х	Х	X :	X	Х	Х	Х	Х	Х	Х	х	Х	Х	Х	Х	х	Х	Х	Х	Х	Х	Х
ERT Administration Log	X	X	X		X	Х	Х	х	X	X :	x	Х	Х	Х	Х	Х	Х	X	Х	Х	Х	х	х	Х	х	Х	X	Х	X
JROM (b)		X				Τ	Τ	П	す		寸	一	х						х			х		х		х	$\top$	Х	X
Neurologic Cranial Nerve Exam and Muscle Strength Testing of Upper Extremities (b)		x				Γ							x						x			x		x		x		x	x
12-Lead ECG	X	X			X	Τ	Τ	П	す	T	┪	一	Х						Х			х		Х		Х	十	Х	X
ЕСНО	X					Τ	T	П	o	$\top$	╅	$\neg$							Х			П		Х	一	$\neg$	$\top$	Х	Х
Chest X-ray	X					Τ	Τ	П	す	T	┪	一							П			П		ヿ			十		
Pregnancy Test (c)	X	X	X			Τ	Х			X :			х			Х			Х			П		$\neg$	$\neg$	$\neg$	$\top$		
Clinical Laboratory Tests	X	X		X		Х	Х	х	х	X :	x	Х	Х			Х			Х		Х	х	х	Х	х	Х	X	Х	X
Liver Panel (d)	X	X			Х(	e)						$\neg$	х	Х	Х	Х	Х	х	Х	Х	Х	х	х	Х	х	Х	Х	Х	Х
MPS II Gene Sequencing (f)	X					Γ	Π	П	Т		П	$\neg$							П			П		$\neg$			T		
SNP Analysis (f)	X					Τ	Τ	П	$\top$	$\top$	╅	$\neg$							П			П		$\neg$		$\neg$	$\top$		
Viral Load	X					Γ	Γ	П	丁	T	T	$\neg$							П			П		$\neg$			T		
Neutralizing Antibodies to AAV2/6	X					Τ	Τ	П	$\top$	$\top$	╅	$\neg$							П			П		$\neg$		$\neg$	$\top$		
GAG Testing in Urine	X (g)	X				Х	Х	х	X	X :	x	Х	Х	Х	Х	Х	Х	X	Х	Х	Х	х	х	Х	Х	Х	X	Х	X
IDS/GAG Testing in Blood (h)	X	X				Х	Х	Х	Х	X :	X	Х	х			Х			х		Х	х	Х	х	Х	х	X	Х	Х
Circulating AFP	X					T	х	П	Х	X	$\dashv$	$\dashv$	х			Π			х		П	х	$\neg$	х	$\dashv$	х	十	х	Х
Vector Genome PCR in Plasma				X (12 hr post- infusion)																									
Vector Genome PCR in Plasma, Saliva, Urine, Stool, and Semen (i)		Х			х	х	x		х	X	x	х	х			x			x										
PFTs (b)	X	X									T		х						х			х		х		х	$\Box$	Х	X
6MWT (b)		X						П			$\exists$		х						х			х		Х		Х	丁	Х	X

CONFIDENTIAL Page 23 of 28

			Hospital or		Day								W	Veek							П			M	font	1			
PROCEDURE	Screening (p)	Baseline	Acute Faci	Care	7	2	4	6	8 1	2 1	6 20	2	24 2	28±	32*	36	40*	44*	48	52*	15	18	21	24	27	30	33	36 EOS	EIV
	(win 3 months of Baseline)	(win 21 days prior to SB-913 infusion)	Day 0	Day 1	(+/-1 day)	(+	+/-2 6	lays)						(	+/-1 w	eek)						(+/-1 month)							
VABS-II	X	X										3	X						X			Х		X		X		X	X
Neurocognitive Abilities Assessment	x																												
Neurocognitive Abilities Testing (j)		х										3	x						x			x		x		x		x	x
MRI of Liver	X						П					3	X						Х			х		Х		Х		X	X
MRI of Brain and Cervical Spine (k)		x																	x					x				X	x
ACTH Stimulation (Cosyntropin) Test (1)		X (prior to prednisone)									х																		
Liver Biopsy (m)		X					П					3	X						Х										
Lumbar Puncture (m)		х										3	x						x										
Immunogenicity Assays (n)		х					x		Z	2		3	x			x			x			x		x					
Prednisone (or equivalent corticosteroid) Administration (o)		х	х				X		•		•																		
SB-913 Infusion			X				П	П		Т		T																	

CONFIDENTIAL Page 24 of 28

\* Week 28, 32, 40, 44, and 52 study visits have assessments that do not require evaluation at the clinical site, and therefore may be conducted at home if the subject is remote. Blood and urine samples at these visits may be collected by a qualified home health nurse. Assessments for AEs, concomitant medications and ERT administration log may be conducted remotely over the phone by study staff.

- § Study subjects may participate in the LTFU Study after 12 months of follow-up in this study, in which case an EOS visit may be conducted any time after Week 52 but before the next scheduled study visit. Study participants who wish to enroll in the LTFU Study with less than 12 months of follow-up in this primary study may be considered on a case-by-case basis at the judgement of the Principal Investigator and after consultation with the Sponsor. In these cases, the EOS visit may be conducted at any time on this study.
- a. Vital signs (height, weight, systolic/diastolic blood pressure, heart rate, respiratory rate, and temperature; for frequency, refer to the Study Reference Manual).
- b. As permitted by subject's capacity.
- c. Serum pregnancy test will be performed at Screening and Baseline visits. Urine pregnancy test will be performed on the Day 0 visit if >7 days from Baseline pregnancy test. Urine pregnancy tests will be performed until Week 48 or until 3 consecutive plasma samples are negative for AAV2/6, whichever occurs first.
- d. Liver panel does not need to be drawn as a separate sample if samples for Clinical Laboratory Tests are obtained at the same visit.
- e. Liver panel will be performed twice a week for the first 20 weeks post-SB-913 infusion, and may be conducted at home if the subject is remote. Blood samples will be drawn 2-4 days apart when possible, except for the first week when it will be drawn on the Day 1 and Day 7 visits. Liver function tests will subsequently be conducted at all indicated study visits.
- f. For adult subjects (cohorts 1 through 4), the assay will be performed on blood or saliva samples; for pediatric subjects (cohorts 5 through 8), saliva samples are preferred.
- g. During Screening, samples for GAG testing in urine will be collected on 3 separate days, each collection occurring at least 7 days after the previous. All samples for GAG testing in the urine must be collected at least 7 days after ERT administration [+/-1 day] but prior to the next ERT infusion.
- h. For IDS/GAG testing in blood, samples must be obtained 7 days after ERT administration (+/- 1 day) and prior to the next ERT infusion. GAG and IDS levels in blood will both be measured concurrently from the same blood sample.
- i. Each type of sample (plasma, saliva, urine, stool, semen) will be collected until 3 consecutive specimens of that sample type are reported as negative or undetectable for vector genome. Collection of semen samples may be waived for male pediatric subjects (cohorts 5 through 8) at the discretion of Principal Investigator.
- j. As permitted by subject's capacity. Neurocognitive abilities testing in pediatric subjects will be done by VABS-II and by WASI-II, WPPSI-IV, or BSID-III, as appropriate based on the Neurocognitive Abilities Assessment performed at Screening.
- k. Baseline MRI of brain and cervical spine may be obtained at the Screening visit (together with MRI for liver) instead of at the Baseline visit at Principal Investigator's discretion.
- 1. Should prednisone or equivalent corticosteroid treatment be continued or repeated due to increased transaminase activity, the ACTH stimulation test will be repeated at the end of taper. Vital signs should be monitored and recorded every hour during the ACTH stimulation test.
- m. Unless contraindicated by a Principal Investigator or physician.

CONFIDENTIAL Page 25 of 28

- n. May be waived for pediatric subjects (cohorts 5 through 8) at the discretion of the Principal Investigator to minimize required blood volumes.
- o. See Appendix 3.
- p. For subjects who are re-screening for participation in the study, assessments including ECHO, chest X-Ray, PFTs, and MRI of liver and/or brain and cervical spine performed for the Screening of a subject in the previous 6 months may be used for evaluation of inclusion/exclusion criteria at the judgement of the Principal Investigator. Further, genetic marker analysis including SNP analysis and MPS II sequencing will not be repeated as results of these assessments do not change over time.

CONFIDENTIAL Page 26 of 28

